Clinical status assessment per WHO 9-point scale ⁶		X	X	X	X	X	X	X	X	X	X	X	X	X	X	
Viral presence and viral load by central testing ⁷		X	X (sentinel only) ⁷	X (sentinel only) ⁷	X (sentinel only) ⁷			X							X	
Confirmation of COVID-19 diagnosis by PCR	X ²	X (PR) ²														

Assessment ¹	Time point	SCR	Treatment Period											FU ¹⁴		ET
			-3d to -1d	D1 (base-line)	D2	D3	D4	D5	D6	D7	D8	D10	D12	D14	D21 (± 3d)	D28 (± 3d)
Oxygenation and FiO ₂ ⁸		X	X	X	X	X	X	X	X	X	X	X	X	X	X	X
Safety assessments:																
Physical examination		X														X
Weight/height ⁹		X													X	X
Hematology, chemistry safety labs ⁶		X	X	X			X			X	X			X	X	X
CRP ⁶		X														
Urinalysis ¹⁰		X								X						
Urine or serum β-hCG (female subjects only)		X ¹¹												X		X
ECG ¹²		X								X						
HR, BP, RR, temperature ⁸		X	X	X	X	X	X	X	X	X	X	X	X			X
(S)AEs ¹³								X								X
Concomitant medications (including SOC)										X						X

AE = adverse event; BP = blood pressure; COVID-19 = novel coronavirus; HR = heart rate; P = pre dose; PAO₂ = partial pressure of oxygen; PR – pre-randomization; RR = respiratory rate; sent = sentinel; SOC = standard of care; SCR = screening.

Note: All screening assessments are to be performed before dosing. If procedures required at any time point have already been performed as part of routine clinical care, these assessments do not need to be repeated, and information will be collected and entered on the eCRF from the subject's medical records. Unscheduled visits can take place at any time at the discretion of the site to check for new AEs/SAEs or to repeat key missed assessments or for other reasons.

¹ The order of assessments can be performed at the discretion of the investigator once informed consent is obtained.

² COVID-19 diagnosis to be confirmed by local testing (PCR) before randomization and first dosing. Saliva, swab, or sputum testing may be used based on local standard of care.

³ To be performed while hospitalized based on standard-of-care local assessment. Evidence of pulmonary involvement consistent with COVID-19 may also be obtained from clinical examination, per the judgment of the investigator. Evidence of pulmonary involvement obtained by clinical examination should be documented in the eCRF.

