⁴ PK assessments will be performed as a substudy in all sentinel subjects. For those subjects requiring dialysis, a single pre- and post-dialysis PK should be obtained for review by the DMC to decide if dose adjustment is needed. PK should be measured weekly for 2 weeks at C_{max} (4-5 hours post dose) for subjects with renal insufficiency when possible.

⁶ Assessments for clinical/respiratory status, progression, and safety serum chemistry and hematology tests to be performed and samples to be collected while hospitalized based on standard-of-care local laboratory assessments and after discharge from the hospital by home visit or outpatient clinic visit or telemedicine call. For subjects who are discharged to home or other outpatient setting after initial hospitalization, the assessments and laboratory samples can be obtained less often but not less than at least once weekly. CRP result required to determine eligibility are based on local laboratory results at screening.

⁷ Viral load testing will be collected daily for the first 4 days using central testing in the first 10 enrolled subjects as part of the sentinel safety assessment at select sites. For all subjects, including the sentinel subjects, swabs, saliva, or other sample collection (as specified in the Study Manual) for central viral load testing will be collected on D1 pretreatment and on D7 or earlier if being discharged from the hospital prior to D7.

Fulcrum Therapeutics
Protocol FIS-001-2020

Losmapimod

⁸ Vital signs will be performed after subjects have been supine for at least 5 minutes when possible. Vital signs to include oxygen saturation; PaO₂ should be recorded if available from blood gases obtained as part of SOC; oxygen administration should also be recorded (eg, room air or oxygen flow by nasal canula or facial mask or endotracheal tube). For subjects who are discharged to home or other outpatient setting after initial hospitalization, assessments may be obtained less often but at least once per week in the outpatient clinic or at home.

⁹ Height assessed at screening only; can be by self-report or from medical records. Weight is an actual recording.

¹⁰ Urinalysis will be performed during the study period only on Day 7 and on any other day only if clinically indicated.

¹¹ Pregnancy testing to be conducted within 72 hours of the first dose of study treatment.

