4 STUDY POPULATION

4.1 Inclusion criteria

Eligible subjects must meet all of the following inclusion criteria at screening.

1. Able and willing to provide written informed consent.
 - a. Note: Subject's legally authorized representative may provide informed consent as applicable based on local guidelines and regulations (see [Section 9.1.3](#)). If consent is obtained from a legally authorized representative, then assent should be obtained from the subject.
2. Willing and able to comply with all study procedures.
3. Age ≥ 40 years at time of screening.
4. Confirmed infection with SARS-CoV-2 virus at or before the baseline visit (by polymerase chain reaction [PCR] testing).
 - a. Note: Refer to the Study Manual for details on PCR SARS-CoV-2 testing procedures.
5. ≤ 7 days to the time of randomization from the time of collection of the specimen that tested positive for the SARS-CoV-2 virus.
6. Hospitalization at the time of the baseline visit.
7. Oxygen saturation $\geq 92\%$ at the baseline visit, which can be either on room air or on oxygen supplementation if using $\leq 10\text{LPM}$ by nasal prong or close-fitting mask.
8. Evidence of pulmonary involvement consistent with COVID-19 by either clinical examination or radiographic examination (whichever is per local standard of care), per the judgment of the investigator. Evidence of pulmonary involvement obtained by clinical examination should be documented in the eCRF.
9. Clinical syndrome consistent with COVID-19 at screening, per the judgment of the investigator ([CDC 2020](#)).
10. CRP at screening $>15 \text{ mg/L}$ (which is equivalent to $>1.5 \text{ mg/dL}$) on local laboratory testing.
11. Agrees to practice an approved method of birth control as follows (as applicable to local [country] guidelines and regulations for sites outside the US):
 - a. Females of childbearing potential: Using 1 of the following acceptable methods of contraception: surgical sterilization (eg, bilateral tubal ligation), intrauterine contraception/device, hormonal contraception, or any 2 barrier methods (a combination of male or female condom with diaphragm, sponge, or cervical cap). This criterion must be followed from the time of the first dose of study medication until 90 days after last dose

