3.2 Analysis Populations

3.2.1 Full Analysis Set (FAS)

The FAS will consist of all subjects who are randomized and receive any study drug. All analyses using the FAS will group subjects according to randomized treatment. The primary endpoint, clinical outcomes/status, survival, and pharmacodynamic endpoints will be analyzed using the FAS. The IA will be based on FAS.

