Change from baseline in viral RNA will be summarized by treatment arm and also analyzed using an analysis of covariance (ANCOVA) model with fixed effects of treatment, and stratification factors, sex and baseline CRP as covariates.

Death is not considered a form of missing data or censoring. The proportion of subjects with clearance of quantifiable viral RNA by Day 7 is calculated by the number of subjects with clearance of quantifiable viral RNA by Day 7 divided by the sum of the number of subjects who is in study by Day 7 and the number of subjects died by Day 7.

The endpoint of comparing percentage of subjects discharged from the hospital, all-cause mortality by Day 28, incidence of AEs/SAEs, incidence of clinically significant changes, and percentage of subjects with clearance of quantifiable viral RNA by Day 7 between treatment groups will be analyzed similarly as the primary endpoint.

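### Viral clearance by Day 7 is neither defined nor conditioned on quantifiable RNA at Day 1, so the risk difference may be attenuated

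*SAP*

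**What the plan says.** SAP Section 3.4.2 builds the clearance proportion from the count of subjects who clear, "divided by the sum of the number of subjects who is in study by Day 7"; deaths up to that day are added to the denominator. Death is explicitly not treated as missing data. The arms are compared by an adjusted risk difference from a logistic model with the stratification factors, sex and baseline CRP as covariates. Baseline viral RNA is not among them.

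The analysis set adds no condition on viral RNA. SAP Section 3.2.1 reads: "The FAS will consist of all subjects who are randomized and receive any study drug".

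Two different samples are involved:

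- **Entry.** Protocol Section 4.1, criterion 5, allows up to 7 "days to the time of randomization from the time of collection of the specimen that tested positive". Footnote 2 to Table 1 adds: "COVID-19 diagnosis to be confirmed by local testing (PCR) before randomization and first dosing". Saliva, swab or sputum may be used.
- **Endpoint.** Footnote 7 to Table 1 says that samples for the central assay "will be collected on D1 pretreatment and on D7 or earlier if being discharged from the hospital prior to D7".

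The objectives tables (Protocol Section 2, SAP Section 2.1) list the endpoint only as quantifiable viral RNA on Day 7. SAP Section 3.4.2 also plans an ANCOVA of change from baseline in viral RNA.

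**The concern.** In its ordinary sense, clearance needs something to clear: RNA quantifiable at the start and not quantifiable later. The entry specimen can be a week old, is tested locally and may be of a different type from the central Day 1 sample. A fully eligible subject can therefore be unquantifiable on Day 1, and no criterion prevents it. That subject still enters the denominator.

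If such subjects are scored the same way in both arms, they add nothing to the difference between arms but still count in both denominators. The risk difference, which is the SAP's chosen effect measure, moves toward zero. This is the only endpoint listed under the objective on SARS-CoV-2 infection, so what is at stake is how clearly the trial can show an effect on the virus. The primary result is not involved.

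**Working it through.** **Plan's own figure.** The documents give no clearance rate, effect size or power for this endpoint, so there is nothing to reproduce on the point itself. As a check on the type of power formula, the primary-endpoint assumptions (30% versus 18%, 205 per arm, one-sided 0.025) give 81.4% in a fixed design with pooled variance. The plan states approximately 80%, with a futility look.

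**Inputs from the documents.** 205 per arm (SAP Section 2.2.4), used only for illustration; one-sided 0.025 (SAP Section 3.1.4); the denominator rule and effect measure (SAP Section 3.4.2).

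**Inputs assumed.** The share q unquantifiable at Day 1 is 10%, 20% or 30%, balanced between arms by randomization. Clearance among the rest is pc = 40% on placebo and pt = 55% on losmapimod.

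**Algebra.** Let s be the share of Day 1 unquantifiable subjects scored as cleared, the same in both arms. The rate in an arm is (1 − q)p + qs. The qs term cancels, so the difference is (1 − q)(pt − pc) for any s. With s = 0 (not cleared) the rates fall; with s = 1 (cleared) they rise.

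**Power.** Normal approximation with unpooled variance, without covariate adjustment: Φ(|d| / SE − 1.96), where SE = √[(p1(1 − p1) + p2(1 − p2)) / n]. Here n is 205 for the SAP denominator and 205(1 − q) for subjects quantifiable at Day 1.

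Example at q = 20%:

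- Quantifiable only: n = 164, SE = √[(0.2400 + 0.2475)/164] = 0.0545, 0.15/0.0545 = 2.75, power 78.6%.
- SAP denominator, not cleared: 32% versus 44%, SE = √[(0.2176 + 0.2464)/205] = 0.0476, 0.12/0.0476 = 2.52, power 71.3%.
- SAP denominator, cleared: 52% versus 64%, SE = √[(0.2496 + 0.2304)/205] = 0.0484, 0.12/0.0484 = 2.48, power 69.8%.

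| q | SAP rates if not cleared | SAP rates if cleared | Difference (points) | Power, quantifiable only | Power, SAP (not cleared / cleared) |
|---|---|---|---|---|---|
| 10% | 36.0% v 49.5% | 46.0% v 59.5% | 13.5 | 83.1% | 79.6% / 78.9% |
| 20% | 32.0% v 44.0% | 52.0% v 64.0% | 12.0 | 78.6% | 71.3% / 69.8% |
| 30% | 28.0% v 38.5% | 58.0% v 68.5% | 10.5 | 73.0% | 62.2% / 60.2% |

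The power loss is 3.5 to 4.2 points at q = 10%, 7.3 to 8.8 at 20% and 10.8 to 12.8 at 30%. Pooled variance changes each power by less than 1 point. The comparison already charges the quantifiable-only analysis for its smaller n.

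**Other assumed rates (pooled variance, q = 20%).** For 30% versus 45%, power is 80.4% against 75.7% / 68.2%. For 60% versus 73%, it is 70.5% against 56.0% / 66.3%. The factor (1 − q) is the same throughout, but the power loss depends on the rates: for 60% versus 73% at q = 30% it reaches 64.8 − 45.5 = 19.3 points.

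**Relative measure.** If these subjects count as not cleared, the ratio of rates does not change (55/40 = 44/32 = 1.375). Only the absolute difference shrinks.

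**The case against.** - **q is unknown.** The documents show that unquantifiable Day 1 samples are possible, not that they occur. If q = 0 there is no effect. This stands, and the sizes above are illustrations.
- **The listed endpoint is a Day 7 status.** For quantifiable RNA on Day 7, an all-treated denominator is natural and matches the FAS. Conditioning on Day 1 changes the question asked. A Day 1 unquantifiable subject could also be quantifiable at Day 7; if treatment altered that chance, such subjects would carry some information and (1 − q) would not be exact. This stands as an argument for keeping the all-subject proportion as a supplement. It does not settle the SAP text, which speaks of clearance without defining it.
- **The objective is partly covered elsewhere.** The ANCOVA of change in viral RNA uses baseline values, and SAP Section 3.3.4 summarizes central Day 1 viral load, so readers may be able to judge q. This lowers the weight of the point but leaves the clearance proportion as it is.
- **A definition may exist elsewhere.** SAP Section 3.4.3 and Appendices A and B are not in the available text, and programming specifications are a separate document. This cannot be ruled out.

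A reader might infer that the plan understates clearance rates, or that the comparison is invalid. The documents support neither. The rates rise if unquantifiable subjects count as cleared. Under the null the expected rates are equal in both arms whatever q is, so false positives are not inflated.

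**Conclusion.** The point holds as a minor one. The clearance proportion is not conditioned on Day 1 RNA, the available text does not define clearance, and the entry rules allow subjects who are unquantifiable on the central Day 1 sample. If a share q of subjects is in that position and is scored alike in both arms, the risk difference is attenuated by (1 − q) under either scoring. With q of 10% to 30% and 40% versus 55%, all assumed, 15 points become 13.5 to 10.5, and power is about 4 to 13 points below that of an analysis in quantifiable subjects.

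The error is toward no effect. The endpoint lies outside the fixed sequence in SAP Section 3.1.5, so no confirmatory claim depends on it and the primary conclusion is unaffected.

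**What to change.** Amend SAP Section 3.4.2 as follows:

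1. Define clearance as quantifiable RNA on the central Day 1 sample and no quantifiable RNA by Day 7.
2. Make FAS subjects with quantifiable central RNA at Day 1 the main analysis, with deaths by Day 7 counted as not cleared. Day 1 status is measured before treatment, so the randomized comparison is kept.
3. State how a missing Day 1 sample is handled, for example by exclusion from the main analysis, with the number per arm reported. State also how a subject still in study without a Day 7 or pre-discharge sample is scored, since the present sentence leaves this open.
4. Report the number unquantifiable at Day 1 per arm, and give the all-subject proportion as a supplement.

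The cost is a short SAP paragraph and one extra table. No new data are needed, because the Day 1 central sample is already collected. The downside is a smaller denominator; in the scenarios above, the undiluted difference more than offsets it.

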3 STATISTICAL METHODOLOGY

3.1 General Considerations

3.1.1 *Analysis Day*

Analysis day will be calculated from the date of first dose of study drug. The day of the first dose of study drug will be Day 1, and the day immediately before Day 1 will be Day -1. There will be no Day 0.

3.1.2 *Definition of Baseline*

Baseline is defined as the last measurement prior to the first dose of study drug.

3.1.3 *Summary Statistics*

Categorical data will generally be summarized with counts and percentages of subjects. The denominator used for the percentage calculation will be clearly stated. Continuous data will generally be summarized with descriptive statistics including n (number of non-missing values), mean (with its standard error), first quartile, median, third quartile, standard deviation, minimum, and maximum.

Where appropriate, descriptive statistics may be presented with 95% CI.

3.1.4 *Hypothesis Testing*

All statistical comparisons will be made using one-sided tests at $\alpha = 0.025$. All null hypotheses will be of no treatment difference, and all alternative hypotheses will be one-sided. Confidence intervals will be 2-sided with $\alpha = 0.05$ and reported to the same precision as the applicable summary statistic (e.g., mean), and standard error will be reported to one additional decimal place. P-values will be reported to four decimal places, with p-values less than 0.0001 reported as "<0.0001".

3.1.5 *Type I Error for Testing Key Study Endpoints*

The overall Type I error of the study will be controlled at 0.025 for 1-sided tests of hypotheses for the following key study endpoints, using a closed test procedure. The key endpoints will be tested in the fixed sequence procedure as the same sequence they are listed below. Assuming the analysis of the prior endpoint yields statistically significant treatment effect, the next key endpoint will be tested.

1. Proportion of progressors to death or respiratory failure by Day 28
2. Change in clinical status using the 9-point WHO scale at Day 14
3. Change in clinical status using the 9-point WHO scale at Day 7
4. Oxygen-free days by Day 28

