3.1.8 Handling of Dropouts and Missing Data

All missing or incomplete safety and PD data, including dates and times, will be treated as such. Missing test results or assessments will not be imputed, and as such, are assumed missing completely-at-random (MCAR).

For laboratory data, values below the limit of quantitation (recorded as “< LLQ”) will be set to half that limit.

For the analysis of hospital-free and ICU-free days, subjects who die prior to the analysis time point will have post-death days considered to be not hospital-free and not ICU-free.

Adverse events with missing start dates will be considered as treatment-emergent unless the partial date excludes that possibility, e.g., the adverse event month is prior to the first dose of study drug. Otherwise, the first day of the month will be used to impute missing start days and January will be used to impute missing start months. For example, if the first dose of study drug was on January 8, 2021 and an adverse event started in January 2021 with missing day, the start date will be imputed as the first dose date (January 8, 2021) and this adverse event will be considered as treatment-emergent. In the same example, if another adverse event has start month of December 2020 with missing day (before the first dose date of January 8, 2021), its start date will be imputed as December 1, 2020 and will not be considered as treatment-emergent.

Subjects who terminate the study prior to the analysis time point, not due to death, will be considered as missing for the analysis of key efficacy endpoints. Missing data in each treatment arm will be imputed using the observed data in their respective arm under the missing at random (MAR) assumption. Multiple imputation (MI) will be performed using the fully conditional specification (FCS) model. The imputation model will include the stratification factors, sex, and baseline CRP.

The handling of missing data for the key efficacy endpoints are outlined as the following:

1. Primary endpoint: patients whose status could not be ascertained (lost-to-follow up, etc.) will be imputed using multiple imputation approach.
2. Change in Clinical Status at Days 7 and 14: missing clinical status at the post-baseline timepoint will be imputed using multiple imputation approach.

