3.2.2 Safety Analysis Set

The Safety Analysis Set is defined as all subjects who receive any study drug. All analyses using the Safety Analysis Set will group subjects according to treatment actually received. The Safety Analysis Set will be used for all safety and tolerability analyses.

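### SAP 3.4.2 puts AE/SAE incidence and clinically significant changes under a primary-style comparison, while SAP 3.1.4 makes every test one-sided with no exception for safety

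*SAP*

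**What the plan says.** The last paragraph of SAP 3.4.2 lists hospital discharge, then "all-cause mortality by Day 28, incidence of AEs/SAEs, incidence of clinically significant changes", then viral RNA clearance, and says that these comparisons "between treatment groups will be analyzed similarly as the primary endpoint".

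The primary analysis (SAP 3.4.1.1) is a risk difference from a logistic model adjusted for the stratification factors, sex and baseline CRP. Its alternative is p_t - p_c < 0. It uses the FAS by randomised arm (SAP 3.2.1), with multiple imputation of unknown outcomes. The pooled result comes with a 95% CI and a 2-sided p-value.

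The general rules in SAP 3.1.4 are "All statistical comparisons will be made using one-sided tests" at 0.025, "all alternative hypotheses will be one-sided", and "Confidence intervals will be 2-sided".

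For safety, the SAP elsewhere says:

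- SAP 3.1.8: missing safety data stay missing, and "Missing test results or assessments will not be imputed".
- SAP 3.2.2: "The Safety Analysis Set will be used for all safety and tolerability analyses", grouped by treatment received.
- SAP 3.4.2, endpoint paragraphs: AE/SAE incidence is given as percentages, and clinically significant changes as per-arm percentages with 2-sided Clopper-Pearson intervals. The denominator for both is completers plus deaths. Protocol 8.7 plans the same summaries but gives no denominator.

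**The concern.** A safety comparison has to be able to point towards harm. The primary test was built to show fewer events on losmapimod. Borrowing it for adverse events, under a general rule that every test is one-sided, produces a p-value that rises towards 1 as the excess on losmapimod grows. A reader of a safety table could take a p of 0.99 as reassurance.

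The sentence also leaves a programmer with competing instructions on whether to make a formal between-arm comparison at all, which analysis set to use, and how to treat subjects who leave early. Safety and tolerability is a stated secondary objective. SAP Section 6, which lists departures from the protocol, does not mention a formal safety comparison.

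**Working it through.** **1. The plan's own figure for the borrowed test.** Inputs from SAP 2.2.4 and Table 2: rates 0.30 and 0.18, 205 per arm, one-sided 0.025, futility bound z = -0.67873 at 103 per arm, final bound z = -1.91358.

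- Variance term: 0.30×0.70 + 0.18×0.82 = 0.3576.
- Expected |z| at the final analysis: 0.12/√(0.3576/205) = 2.873. At the interim: 0.12/√(0.3576/103) = 2.037.
- Bivariate normal calculation with correlation √(103/205): power 80.2% (79.4% with pooled variance), one-sided alpha 0.0250, probability of a futility stop under the null 0.751.

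These agree with the stated 80%, 0.025 and about 0.75. The primary design is therefore a one-sided test towards fewer events on losmapimod, and nothing below changes its alpha or sample size.

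**2. The same direction applied to an excess of SAEs.** The documents give no expected SAE rates, so the rates here are assumptions: 20% on losmapimod, 12% on placebo, 205 per arm, no covariates.

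- SE = √(0.20×0.80/205 + 0.12×0.88/205) = √(0.2656/205) = 0.0360.
- z = 0.08/0.0360 = +2.22.
- One-sided p for p_t - p_c < 0: Φ(2.22) = 0.987.
- 2-sided p: 2×(1 - Φ(2.22)) = 0.026.
- 95% CI: 0.08 ± 1.96×0.0360, or +0.9 to +15.1 points.

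The same formulas over a range of assumed rates:

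| Placebo | Losmapimod | z | One-sided p | 2-sided p | 95% CI (points) |
|---|---|---|---|---|---|
| 10% | 20% | 2.86 | 0.998 | 0.004 | +3.2 to +16.8 |
| 20% | 30% | 2.35 | 0.991 | 0.019 | +1.7 to +18.3 |
| 30% | 42% | 2.55 | 0.995 | 0.011 | +2.8 to +21.2 |
| 50% | 60% | 2.05 | 0.980 | 0.041 | +0.4 to +19.6 |

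The pattern does not depend on the rates chosen: with this direction, any observed excess gives a one-sided p above 0.5. In every row the 2-sided interval excludes zero.

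**3. The passages side by side.**

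| Question | Closing sentence of SAP 3.4.2 with the primary analysis | Rest of the documents |
|---|---|---|
| Type of analysis | Adjusted between-arm risk difference | Percentages; per-arm intervals for clinically significant changes (SAP 3.4.2, protocol 8.7) |
| Analysis set | FAS by randomised arm, if carried over | Safety Analysis Set by treatment received (SAP 3.2.2) |
| Missing data | Multiple imputation, if carried over | Not imputed (SAP 3.1.8); completers plus deaths as denominator (SAP 3.4.2) |
| Sidedness of p-value | One-sided (3.1.4), or 2-sided after pooling (3.4.1.1) | Not stated separately for safety |

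**4. The denominator.** Leaving non-death dropouts out of the denominator while keeping their events in the numerator raises the percentage. With 62 of 205 subjects having an AE (30.2%) and assumed dropout of 4, 10 or 20 subjects (about 2%, 5%, 10%): 62/201 = 30.8%, 62/195 = 31.8%, 62/185 = 33.5%. This distortion comes from exclusion, not from imputation.

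**The case against.** The strongest reply is that the sentence borrows only the estimator. It also covers discharge and viral clearance, where a higher rate is favourable; carrying p_t - p_c < 0 over literally would test those for losmapimod being worse. So direction is probably not part of what is borrowed, and no passage states one for safety. That stands, and it makes the direction an inference. It does not clear the text: 3.1.4 still requires a one-sided alternative, and carrying over either the sign or the idea of benefit leads to fewer adverse events.

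A reader might infer that harm could not be detected. The documents do not support that. Intervals are 2-sided, and the pooled primary analysis reports a 2-sided p-value, which would be 0.026 in the example. AE, SAE and special-interest event tables (SAP 3.5.1) and ongoing DMC safety review (SAP Section 4) do not depend on this sentence.

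A reader might also infer that adverse events nobody observed would be imputed. The SAP does not specify that. SAP 3.1.8 rules it out for safety data and directs multiple imputation at the key efficacy endpoints. The extension of imputation in 3.4.2 covers only the endpoints above it, and the safety paragraphs follow it. Those paragraphs leave non-death dropouts out rather than filling them in. What remains is a possible misreading of the closing sentence. Some text after the imputation model is redacted and the sample code is not shown, so the programmed intent cannot be checked.

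On the analysis set, SAP 3.2.2 is explicit, and both sets require dosing. Among randomised subjects they differ only in how anyone given the wrong treatment is grouped, so the practical effect is small.

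**Conclusion.** The concern holds as a conflict in the SAP with a specific remedy. Two safety endpoints are placed under a formal primary-style comparison, and a blanket one-sided rule then applies to them without exception. If the primary direction is carried over, an excess of 8 to 12 points on losmapimod gives one-sided p-values of 0.980 to 0.998, against 2-sided values of 0.004 to 0.041. These figures assume the stated safety rates, 205 per arm and an unadjusted comparison.

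The risk is a misleading p-value and inconsistent programming. It is not concealed harm, because the 2-sided intervals and 2-sided pooled p-value would show the excess, and it is not imputed adverse events. The safety endpoints lie outside the testing hierarchy in SAP 3.1.5, so alpha, power and the primary conclusion are unaffected. The change is still worth making, because a one-sided rule is wrong for safety as it stands.

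**What to change.** 1. In the closing paragraph of SAP 3.4.2, delete AE/SAE incidence and incidence of clinically significant changes from the list of endpoints compared like the primary.
2. In SAP 3.1.4, state that one-sided testing applies to efficacy endpoints only.
3. In the safety paragraphs of SAP 3.4.2, report both endpoints on the Safety Analysis Set by treatment received, using observed events, with that set as the denominator in place of completers plus deaths. Give a 2-sided 95% CI for the between-arm difference.
4. Record the added between-arm interval and the denominator in SAP Section 6.

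The cost is SAP wording. Sample size, alpha and trial conduct do not change, and the programming becomes simpler.
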